6 PARTICIPANT SAFETY

6.1 Risk, Benefits and Inclusion of Children

The risks of this study are presented in this protocol and in the informed consent form. This study will examine whether ATG will delay or prevent the onset of T1D. As discussed above, there is prospect of direct benefit for participants who are children by participation in this study.

Moreover, our experience in using ATG in people with Stage 3 disease has shown a similar safety profile in adults and children and supports a favorable risk-benefit ratio in children with Stage 2 T1D as discussed above. Assent of children along with consent of the parents or legal guardians will be obtained prior to any study procedures. This research proposal in children is therefore consistent with United States Department of Health and Human Services, Protection of Human Participants, subpart D, section 46.405 (research involving greater than minimal risk but presenting the prospect of direct benefit to individual participants) and with Subpart D. 50.52 (Clinical investigations involving greater than minimal risk but presenting the prospect of direct benefit to individual participants).

6.2 Potential Risks

6.2.1 ATG

ATG has been widely used in transplantation and autoimmune disorders⁴⁷. In the ITN START study, participants received ATG at a total dose of 6.5 mg/kg, a dose which has been effective and well tolerated in bone marrow and solid organ transplantation, and well below the dose of 20 mg/kg that has been used for some transplantation protocols. For this study, the doses will be administered as 0.5 mg/kg during the first infusion and 2 mg/kg during the second infusion to reduce adverse reactions. ATG will be given over at least 6 hours for both infusions. Participants will receive pre-medication with acetaminophen and diphenhydramine (or equivalent) and participants randomized to active therapy will receive methylprednisolone prior to the infusion that contains ATG. This is to minimize side effects from possible cytokine release syndrome (CRS). Participants will be closely observed in the hospital/outpatient setting during the treatment period and will be contacted between treatments for assessment of adverse events and management should they occur. Symptoms of CRS may include fever, chills, rigors, headache, tremor, nausea, vomiting, diarrhea, abdominal pain, muscle and joint pain, and malaise. Anaphylactic reactions have been rarely reported with ATG. Delayed reactions such as serum sickness occur in approximately $\frac{3}{4}$ of actively treated participants between 9-14 days post-infusion. Thrombophlebitis may also develop following infusion with ATG.

ATG contains a variety of antibodies that may cross-react with cell-surface markers. ATG causes lymphocyte depletion with marked depletion of lymphocytes occurring acutely. The circulating number of T cells increases with cessation of therapy, usually reaching pre-treatment levels of CD8+ T cells by 2 months. Participants are at low absolute but relatively increased risk for opportunistic infection during this window of recovery and will receive close surveillance for primary viral infections, viral reactivations, and bacterial infections^{71,72}.

ATG may also lead to leukopenia and thrombocytopenia. Effects are dose-dependent and are mainly encountered with over dosage. In up to 3% severe thrombocytopenia may occur but this is invariably seen in doses 4-5 times that which we are proposing. Thrombocytopenia in these participants often occurred in a postoperative transplant setting and with other immunosuppressants.

Transient abnormalities in liver function tests have been described in people with aplastic anemia treated with ATG preparations. Such adverse events have not been noted in numerous other clinical settings in which ATG has been used, and it is not clear if this is related to the underlying disease or to associated medications used.

Conflicting data exists about the risk of EBV-related lymphoproliferative disease. Furthermore, in people with renal transplant, the overall risk is low (0.25%-0.85%) even though these populations received multiple immunosuppressive therapies and were on continuous immunosuppression (30). There were no reported cases of EBV-associated lymphoproliferative disease in over 1,675 treated participants (including children) treated for aplastic anemia.

Treatment with ATG may increase the risk for serum sickness and may preclude future exposure to rabbit-derived immunotherapeutics including second courses of ATG.

There is the possibility that, instead of delaying or preventing the development of stage 3 type 1 diabetes (clinical diagnosis), ATG could increase the destruction of islet cells in the pancreas. The risk of this happening is unknown. This could cause type 1 diabetes to develop more quickly.

6.2.2 Insertion and Wearing a Continuous Glucose Monitor (CGM)

Inserting and wearing a CGM device may cause mild pain, discomfort, inflammation or irritation from the device, which could be related to the insertion needle or to adhesives and tapes used to secure the CGM device to the skin. Minor risk of infection at the needle insertion site is also possible. The CGM device will be inserted by the investigator or trained staff using techniques designed to minimize the risk of inflammation or infection. Signs and symptoms of skin problems and site infections are to be discussed with each participant.

6.3 COVID-19

ATG is not believed to increase the risk of acquiring COVID-19. However, individuals who have received ATG may be at risk for a more severe clinical course with SARS-CoV2. To mitigate this risk the following precautions will be instituted:

- 1) Those at highest risk for severe COVID-19 infection are excluded from enrollment.
- 2) All participants will be advised to follow country-specific guidelines and recommendations regarding social distancing, masking, and avoiding contact with individuals with COVID-19 within 10 days, crowded spaces for immune compromised individuals.
- 3) Although no live vaccinations will be allowed during this trial, other non-live vaccines such as COVID-19 and influenza are allowed; however, the effectiveness of non-live vaccinations given in the 3 months following the study treatment phase is unknown. Participants are strongly encouraged to be up-to-date on COVID-19 vaccine(s) at least 2 weeks prior to randomization (follow country-specific/regional guidelines). Samples to evaluate response to vaccination may be

collected in such participants. In addition, if future recommendations are issued by the national health governing body regarding COVID-19 vaccinations, the participants will be encouraged to follow them.

All coronavirus-related events are to be reported as adverse events. If the event meets the criteria of a SAE, expedited SAE reporting is to be followed and such events should be reported to the sponsor within timelines.

6.4 Pregnancy

Female participants with reproductive potential will be instructed to use effective means of birth control (which includes abstinence) from randomization until 3 months post second infusion of study drug to assure safety. They will also be asked to avoid pregnancy until the conclusion of the study. This is to assure accurate endpoint measurements. They will undergo urine pregnancy testing at the start of every study visit. All pregnancies that are identified during the study must be followed to conclusion and the outcome of each must be reported. The investigator should be informed immediately of any pregnancy occurring in a female participant. Monitoring of the participant should continue until the conclusion of the pregnancy. Participants that are found to be pregnant while on this study will still be followed for safety and other study measures as appropriate.

All pregnancies within the trial (either the participant female or the participant female partner) should be reported to the external sponsor and Sanofi using the relevant Pregnancy Reporting Form within 24 hours of notification.

Pregnancy is not considered an AE unless a negative or consequential outcome is recorded for the mother or child/fetus. If the outcome meets the serious criteria, this would be considered an SAE (any complication of pregnancy should be reported as a SAE if meeting seriousness criteria: spontaneous abortion (even if no hospitalization), and congenital anomalies.)

Women who required insulin during or shortly after pregnancy but for who, insulin requirements resolved post-partum will not be considered to have previously had stage 3 T1D and will be eligible if all other study inclusion/exclusion criteria are met.

6.5 Protecting Against or Minimizing Potential Treatment Risks

Participants will not be enrolled who have other active serious medical problems. Frequent monitoring with history, physical examination, and laboratory studies will allow for early identification of adverse events. All participants will be required to have adequate hemoglobin to allow safe frequent venipuncture. Every attempt will be made to minimize the number of venipunctures.

All study drug infusions will take place in a facility that has resuscitation capabilities, and participants will be closely monitored during and after the treatment.

Participants will be counseled about the potential risk for infections and the need to report any change in health status between or at the time of visits. Directed questioning about concurrent illness will occur before each infusion. No infusion will occur in those with signs or symptoms indicative of active infection.

7 ADVERSE EVENT REPORTING AND SAFETY MONITORING

7.1 Adverse Event Definition

In this clinical trial, an adverse event is any occurrence or worsening of an undesirable or unintended sign, symptom or disease whether or not associated with the treatment and study procedures.

Throughout the study, the investigator must record all adverse events on source documents. Adverse Events of Special Interest (AESIs) as described in section 7.4 which are Grade 1 or greater per the NCI CTCAE must be reported electronically to the TNCC. Events not related hypoglycemia, or hyperglycemia which are Grade 2 or greater per the NCI CTCAE (see Section 7.6 and 7.7 below) must be reported to TNCC as AE. The investigator should treat participants with adverse events appropriately and observe them at suitable intervals until the events resolve or stabilize.

Adverse events may be discovered through:

- observation of the participant;
- questioning the participant;
- unsolicited complaint by the participant.

Questioning of the participant should be conducted in an objective manner.

7.2 Adverse Reaction

An adverse reaction means any adverse event caused by a drug. Adverse reactions are a subset of all suspected adverse events for which there is reason to conclude that the drug caused the event. Suspected adverse reaction means any adverse event for which there is a reasonable possibility that the drug caused the adverse event. For the purposes of safety reporting, “reasonable possibility” means there is evidence to suggest a causal relationship between the drug and the adverse event. A suspected adverse reaction implies a lesser degree of certainty about causality than an adverse reaction, which means any adverse event caused by a drug. Examples of evidence that suggest a causal relationship (reasonable possibility) between the drug and the adverse event include:

- A single occurrence of an event that is uncommon and known to be strongly associated with drug exposure
- One or more occurrences of an event that is not commonly associated with drug exposure, but is otherwise uncommon in the populations exposed to the drug
- An aggregate analysis of specific events observed in a clinical trial (such as known consequences of the underlying disease or condition under investigation or other events that commonly occur in the study population independent of drug therapy) that indicates those events occur more frequently in the drug treatment group than in a concurrent or historical control group.

7.3 Serious Adverse Event/Reaction

A serious adverse event (SAE) or reaction is defined as “any adverse event occurring at any dose that suggests a significant hazard, contraindication, side effect, or precaution.” An adverse event

or suspected adverse reaction is considered “serious” if, in the view of either the investigator or sponsor, it results in any of the following outcomes:

1. Death. A death that occurs during the study or that comes to the attention of the investigator during the protocol-defined follow-up after the completion of therapy must be reported whether it is considered to be treatment related or not.
2. A life-threatening adverse event. The term life-threatening is defined as (1) diseases or conditions where the likelihood of death is high unless the course of the disease is interrupted and (2) diseases or conditions with potentially fatal outcomes, where the endpoint of clinical trial analysis is survival (21 CFR 312.81(a)).
3. Inpatient hospitalization or prolongation of existing hospitalization with the exception of hospitalization relating to initial diagnosis of stage 3 type 1 diabetes. Symptoms/reactions of stage 3 T1D onset which require intravenous intervention for diabetes management in an emergency room, physician’s office or visiting nurse.
4. Persistent or significant incapacity or substantial disruption of the ability to conduct normal life functions
5. Congenital anomaly or birth defect.
6. Important medical events that may not result in death, be life-threatening, or require hospitalization may be considered serious when, based upon appropriate medical judgment, they may jeopardize the participant and may require medical or surgical intervention to prevent one of the outcomes listed above.

Adverse event or suspected adverse reaction are considered “life-threatening” if they are (1) diseases or conditions where the likelihood of death is high unless the course of the disease is interrupted and (2) diseases or conditions with potentially fatal outcomes, where the endpoint of clinical trial analysis is survival (21 CFR 312.81(a)).

Regardless of the relationship of the adverse event to study drug, the event must be reported as a serious adverse event if it meets any of the above definitions.

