1 INTRODUCTION

1.1 Study Overview

Title	Low-Dose ATG to Delay or Prevent Progression to Stage 3 T1D
IND Sponsor	National Institute of Diabetes and Digestive and Kidney Diseases (NIDDK)
Conducted By	Type 1 Diabetes Trial Network (TrialNet)
Protocol Chair	[name]
Accrual Objective	101
Study Design	A multi-center, placebo-controlled, double blind, 2:1 randomized control clinical trial testing low-dose ATG vs. placebo in participants with a 2-year 50% risk of progression to Stage 3 T1D.
Treatment Description	Participants will receive either low-dose ATG or placebo. Infusions will be given as follows: Day 1 of infusion will be ATG/Placebo at 0.5 mg/kg IV over a minimum of 6 hours. Day 2 of infusion will be ATG/Placebo at 2 mg/kg IV over a minimum of 6 hours. The maximum infusion time is 10 hours.
Study Duration	Enrollment is expected to occur over 4 years. Participants will be followed up for at least 24 months from randomization in this protocol. All participants that progress to Stage 3 T1D will be followed post-diagnosis for at least 12 months. All participants, regardless of T1D status will be followed for at least 12 months following the primary endpoint.
Objective	To determine the ability of low dose ATG to prevent or delay progression to Stage 3 T1D in participants aged 6-35 years with a 2-year 50% risk for progression.
Primary Outcome	The primary outcome is progression to the diagnosis of clinical T1D (Stage 3 T1D).
Secondary Outcomes	The study will also examine the effect of the proposed treatments on metabolic and immunologic markers of diabetes progression, continuous glucose monitoring metrics and adverse event frequency. Samples will be collected for mechanistic, PK and immunogenicity assays.
Major Inclusion Criteria	
Participants will have a 2-year 50% risk for progression to Stage 3 T1D* defined by the presence of at least two biochemical autoantibodies, dysglycemia**, and at least one of the following additional high risk characteristics:
 
 • HbA1c \geq 5.7% and $<$6.5% • Index60 \geq 1.4 • DPTRS \geq 7.4 
*Dysglycemia and at least one high risk characteristic must be present at the same visit within 52 days of randomization.
 
**Dysglycemia (ADA) is defined as 2-hr glucose \geq 140 and $<$200 mg/dL or fasting glucose \geq 110 and $<$126 or 30, 60, or 90 minute \geq 200mg/dL.

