5.8 Interruption of Enrollment/Trial Cessation

This section lists clinical and laboratory adverse events that will necessitate interruption of enrollment in the trial as a whole. As part of their ongoing safety review, the DSMB will make independent judgments regarding other adverse events requiring trial interruption. In addition, should the study be stopped, the FDA will be informed and the study will not resume until both the DSMB and the FDA are in agreement.

1. Any drug related death or Grade 4 SAE; During this trial, any grade 4 SAE death event will be temporarily considered unexpected and potentially drug-related until the event is reported and reviewed by the FDA and DSMB. In this event, the trial will be interrupted, including dosing of participants already enrolled and enrollment of new participants, until the grade 4 SAE or death event is reviewed by both the FDA and DSMB and both agree to the restart of trial enrollment and study agent administration.
2. Severe adverse event (defined in section 7.3) that is possibly, probably or definitely related to study treatment in any of the first 3 participants, or severe adverse events in the same organ system in any 2 participants with the exception of Grade 3 lymphopenia within the first 30 days of drug treatment. This criterion supersedes all rules below (3-8).
3. Occurrence of anaphylaxis during study treatment in any participant. Anaphylaxis is a serious allergic reaction that is rapid in onset and may cause death. Anaphylaxis is highly likely when any one of the following 3 criteria are fulfilled:
 1. Acute onset of an illness (minutes to several hours) with involvement of the skin, mucosal tissue, or both (e.g., generalized hives, pruritus or flushing, swollen lips-tongue-uvula)

AND AT LEAST ONE OF THE FOLLOWING:

 - i. Respiratory compromise (e.g., dyspnea, wheeze-bronchospasm, stridor, reduced peak expiratory flow (PEF), hypoxemia)
 - ii. Reduced Blood Pressure (BP) or associated symptoms of end-organ dysfunction (e.g., hypotonia [collapse], syncope, incontinence)
 2. Two or more of the following that occur rapidly after exposure to a likely allergen for that person (minutes to several hours):
 1. Involvement of the skin-mucosal tissue (e.g., generalized hives, itch-flush, swollen lips-tongue-uvula)
 2. Respiratory compromise (e.g., dyspnea, wheeze-bronchospasm, stridor, reduced PEF, hypoxemia)
 3. Reduced BP or associated symptoms (e.g., hypotonia [collapse], syncope, incontinence)

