7.7 Adverse Event Reporting and Monitoring

The investigator will grade their severity according to common toxicity criteria or study-specific criteria and will decide of their relation to therapy. Events will be assessed and reported consistent with the ICH Guidelines for Good Clinical Practice, 21 CFR 312.32 for expedited safety reporting, and per the guidance of the DHHS Office for Human Research Protections (OHRP). General descriptions of grading are as follows:

- Grade 1 are mild adverse events requiring no specific medical intervention or asymptomatic laboratory findings
- Grade 2 are moderate adverse events, minimal, local, non-invasive intervention
- Grade 3 are severe and undesirable events, significant symptoms requiring hospitalization or invasive intervention
- Grade 4 are life-threatening or disabling events
- Grade 5 are fatal events (death)

The adverse event case report form for the protocol must be completed for all adverse events assessed as grade 2 or higher and grade 1 and higher for AESIs. The investigator is responsible for regular participant follow-up and for ensuring all adverse events are documented and reported appropriately. For reporting serious adverse events (SAE), in addition to the AE case report form, the site should also complete a MedWatch Form and email/fax to the TNCC *within 24 hours of when the site is notified of the event*. This will be reviewed by the TrialNet Medical Monitor and the DSMB as appropriate. Death must be reported immediately. Event outcome and other follow-up information regarding the treatment and resolution of the event will be obtained and reported when available, if not known at the time the event is initially reported. The follow-up information should

contain sufficient detail to allow for a complete medical assessment of the case and an independent determination of possible causality.

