8.1 Primary Outcome and Analyses

The primary outcome is the elapsed time from random treatment assignment to the development of diabetes or time of last contact among those randomized.

Criteria for stage 3 diabetes onset are, as defined by the American Diabetes Association (ADA), based on glucose testing, or the presence of unequivocal hyperglycemia with acute metabolic decompensation (diabetic ketoacidosis) as defined below:

1. Unequivocally symptomatic* AND at least one of the following:

1. Random glucose ≥ 200 mg/dl [11.1 mmol/L] OR
2. Fasting glucose ≥ 126 mg/dl [7 mmol/L] OR
3. OGTT = diabetic OR
4. HbA1c $\geq 6.5\%$

* Unequivocal symptoms: severe/persistent polyuria, polydipsia and/or significant unexplained weight loss

2. If not unequivocally symptomatic, two separate objective measures are required for diagnosis. These tests must occur at least one day apart but as soon as possible and must be consecutive, defined as without an intervening non-diabetic OGTT.

1. The preferred object measures for diagnosis are:

1. 2 diabetic OGTTs, not on the same day (the confirmatory OGTT is the date of diagnosis)
2. However, if an individual is diagnosed without the consecutive OGTTs, the following also constitutes diagnosis in TrialNet:
 1. Diabetic OGTT + FPG ≥ 126 mg/dl [7 mmol/L] not on the same day
 2. Diabetic OGTT + HbA1c $\geq 6.5\%$ (these may be on the same day)
 3. FPG ≥ 126 mg/dl [7 mmol/L] + HbA1c $\geq 6.5\%$ (these may be on the same day)

It is preferred that OGTTs for Stage 3 T1D diagnosis are analyzed using TrialNet laboratories. If a participant has an OGTT that indicates diabetes (clinical alert), the site should invite the participant for a repeat OGTT as soon as possible. To make a diagnosis of Stage 3 T1D diabetes, each of two consecutive OGTTs must meet diabetes criteria. Thus, if the second OGTT does not confirm the diagnosis, the participant will continue to be followed in the ATG Low-Dose Prevention Study and will be asked to return for the next follow-up visit. At that time, the OGTT will be repeated and, if indicative of diabetes, will need to be performed a second time to confirm the diagnosis.

In the case of symptoms or unequivocal hyperglycemia with acute metabolic decompensation (diabetic ketoacidosis), repeat testing is not required to confirm the diagnosis of Stage 3 T1D and prompt evaluation and initiation of clinically indicated treatment will occur.

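### Section 7.3 defines life-threatening by kind of disease and adds a survival-endpoint limb that cannot apply here, so some events may be classified inconsistently as SAEs

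*Combined protocol and SAP*

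**What the plan says.** Section 7.3 (Serious Adverse Event/Reaction) lists six outcomes that make an event serious. Criterion 2 is a life-threatening adverse event. Its first limb is: "The term life-threatening is defined as (1) diseases or conditions where the likelihood of death is high unless the course of the disease is interrupted". The text joining it to the second limb is: "interrupted and (2) diseases or conditions with potentially fatal outcomes, where the endpoint of clinical trial analysis is survival (21 CFR 312.81(a".

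The paragraph after the list restates this as a test. An adverse event or suspected reaction counts as life-threatening "if they are (1) diseases or conditions where the likelihood of death is high unless the course of the disease is interrupted and (2", followed by the same survival-endpoint limb.

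Four other places bear on this:

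- **Endpoint.** Section 1.1: "The primary outcome is progression to the diagnosis of clinical T1D (Stage 3 T1D". Section 8.1: "The primary outcome is the elapsed time from random treatment assignment to the development of diabetes".
- **Grading.** Section 7.7: "Grade 4 are life-threatening or disabling events", with no condition about the trial endpoint.
- **Reporting.** Section 7.7 requires assessment and reporting consistent with, among others, "21 CFR 312.32 for expedited safety reporting", and requires SAEs to reach the coordinating center within 24 hours.
- **Halting.** Rule 1 in section 5.8 opens "Any drug related death or Grade 4 SAE". Rule 2 refers to section 7.3 for the definition of the events that it counts.

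**The concern.** A seriousness criterion should ask what the event did to the participant. Criterion 2 asks what kind of disease is involved, and then adds a condition about the trial's analysis endpoint. That condition is false throughout this trial, whatever happens to a participant.

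The label has consequences. It starts the 24-hour report and the medical monitor's decision on expedited reporting. It also decides whether a Grade 4 event falls under halting rule 1, which stops dosing and enrollment until the FDA and the DSMB have both reviewed the event and agreed to a restart. If the definition can be read in two ways, two sites could give the same reaction different labels, and the halting rule would apply at one site and not at the other.

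**Working it through.** No arithmetic decides this point. The check sets the passages side by side.

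1. **Survival limb against endpoint.** The second limb refers to a trial analyzed for survival. Sections 1.1 and 8.1 give the endpoint as progression, or time, to Stage 3 T1D. The limb is not satisfied for any event in this trial.

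2. **Both limbs required.** The closing paragraph of 7.3 is a conditional test with the limbs joined by *and*. Taken literally, both must hold. Limb (2) never holds, so no event meets criterion 2.

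3. **Limbs as a list.** The sentence inside criterion 2 can also be read as naming two categories, each with its own disease-or-condition phrase. Limb (1) then remains usable and limb (2) is dead text. Limb (1) still tests how lethal the condition is if its course is not interrupted. It does not test whether this event, as it occurred, endangered this participant.

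4. **An event that tests the wording.** Take a Grade 4 cytokine release syndrome (CRS) during an infusion in an inpatient unit, which section 4.1 allows. It resolves on site within 72 hours without lengthening the stay.
   - Criteria 1 and 5 (death, congenital anomaly) do not apply.
   - Criterion 2 depends on the reading chosen in steps 2 and 3.
   - Criterion 3 is not met: there is neither a new admission nor a prolongation.
   - Criteria 4 and 6 are matters of judgment, and criterion 6 is worded as discretionary.
   - The opening sentence of 7.3 is broad enough to include the event, and either the investigator or the sponsor may judge it serious.

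   The event can be called serious, but on judgment and not on a plain criterion.

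5. **Halting rules for the same event.** Rule 4 names Grade 3 CRS unresolved at 72 hours and Grade 2 CRS unresolved at 48 hours, so this event is outside its wording. Rule 3 applies only if there is anaphylaxis. Rule 6 applies only if there is Grade 3 hypotension, urgent care or hospitalization, and only at its stated counts. Rule 1 is then the main single-event trigger, and it needs the SAE label. Rule 2 also depends on 7.3.

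6. **Size.** Section 3.2 assigns 68 participants to ATG, with two infusions each: 68 × 2 = 136 planned ATG infusions. Section 2.3.2 reports CRS in TN19 as a non-serious event in 3 of 10 ATG-only adults (Table 2) and in 11 ATG-only participants aged 12–17 (Table 4). No CRS is listed as serious in either group. The tables give no grades, so they neither establish nor exclude Grade 4 events. No expected count can be derived.

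**The case against.** The strongest reply is that this is clumsy wording with little practical effect. Section 7.1 defines an adverse event as including a disease, and the grammatical subject in 7.3 is the event. An investigator could therefore treat a reaction such as anaphylaxis as a condition likely to be fatal unless interrupted, and criterion 2 would work on limb (1). Most severe reactions during outpatient dosing would reach criterion 3 anyway, because section 4.1 lists Grade 3 events among those that warrant admission. Anaphylaxis interrupts enrollment under rule 3 whatever its SAE status. CRS and anaphylaxis are events of special interest, reported from Grade 1 upward and passed to the drug supplier within one business day. The medical monitor reviews all adverse event reports (section 10.3.5).

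Most of this stands, and it narrows the point. Four stronger inferences should not be drawn:

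- **That life-threatening events could not be serious, or would go unreported.** The opening definition, criteria 1 and 3 to 6, and investigator or sponsor judgment all remain. Section 7.3 makes SAE reporting mandatory if any of its definitions is met.
- **That such an event is serious only through criterion 6.** The same text rules this out.
- **That 7.3 and 7.7 flatly contradict each other.** Section 7.7 describes severity and 7.3 defines seriousness. They use one term in different senses, which calls for reconciliation.
- **That the regulation cited in 7.3 is the wrong one.** The documents do not reproduce either regulation. They show only that the two sections cite different provisions.

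The reply leaves the literal wording of the closing test and the dead survival limb in place. Central review of adverse events may also come later than 24 hours for an event that the site did not label serious.

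**Conclusion.** The point holds in a limited form. Both statements of the definition in 7.3 contain a limb with no application in this trial, and neither asks whether the event endangered the participant. That no event can meet criterion 2 is true only if both limbs are required. The closing test supports that reading, but the sentence in criterion 2 leaves room for the other.

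The exposure is inconsistent SAE classification of life-threatening events that resolve on site without admission or a prolonged stay. These are probably few, though that is a judgment: the documents give no frequency. They matter because one such drug-related event, if Grade 4 and labelled an SAE, interrupts the trial under rule 1. The conclusion rests on the protocol's wording alone, not on the content of the cited regulations. The correction is worth making for safety reporting and does not bear on the efficacy analysis.

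**What to change.** In both places in section 7.3:

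- Replace the definition with an event-level one, for example: an event is life-threatening if, in the view of the investigator or sponsor, the event as it occurred placed the participant at immediate risk of death.
- Delete the survival-endpoint limb.
- Reconcile the regulatory citation with the one that section 7.7 uses for expedited reporting.

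Do not define the criterion as Grade 4. In 7.7 that grade also covers disabling events, and severity is graded separately from seriousness. The halting rules and clinical management need no change for this purpose.

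The cost is two sentences of protocol wording and a note to sites.
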